## 9.5.3 Appropriateness of Measurements

All clinical assessments were standard measurements commonly used in studies of schizophrenia.

The safety assessments performed in the study, including hematology analyses, blood chemistry tests, urinalysis, and assessment of AEs, were standard evaluations to ensure subject safety.

## 9.5.4 Reporting of Serious Adverse Events, Pregnancy, and Other Events of Interest

Collection of safety information was completed from the first administration of the study drug until 28 days after discontinuation, unless otherwise specified in the protocol. The longer of the two timeframes was employed if there was a conflict.

Safety information was defined as any information from any source containing information such as:

- AE or suspicion thereof
- Lack of efficacy
- Overdose/incorrect dosage (i.e., accidental or intentional)
- Abuse/misuse (e.g., patients sharing medication); even without resulting adverse reaction
- Accidental exposure (e.g., child takes parent's medication)
- Medication error
- Withdrawal reactions
- Disease progression/exacerbation of existing disease
- Drug-drug/drug-food interactions
- Exposure to drug during pregnancy, where the embryo or fetus may have been exposed to medicinal products either through maternal exposure or transmission of a medicinal product via semen following paternal exposure
- Exposure to drug during lactation, including uneventful
- Suspected counterfeit product
- Suspected transfer of infectious disease/agent by the medicinal product concerned
- Product Quality Complaint (PQC) with safety related/medically important information
- Pediatric use, if not an approved use

Final; 26 Feb 2018 Page 50 of 80

- Occupational exposure
- Off-label use

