#### 9.1.4.2 Treatment Phase

Eligible subjects who had a history of tolerating oral aripiprazole or were currently taking oral aripiprazole entered Phase B directly from the Screening Period. All other subjects entered Phase B following successful completion of Phase A. After the baseline assessments were completed, the subject received the first aripiprazole once monthly IM injection, in conjunction with the first of 14 doses of concomitant oral antipsychotic medication (see Figure 1). Use of concomitant oral aripiprazole during this lead-in was per the investigator's judgment based on the prescribing instructions.

All subjects must have attended scheduled visits at the Baseline Visit and Weeks 2, 4, 8, 12, 16, 20, and 24, totaling 180 days. Aripiprazole once monthly injections occurred at the Baseline Visit and every 28 (-2, +5) days at Weeks 4, 8, 12, 16, 20, and 24, totaling seven injections. After the

Final; 26 Feb 2018 Page 28 of 80

initial injection of 400 mg, the monthly dosage could be decreased to 300 mg, based on the clinical judgment of the investigator. All aripiprazole once monthly injections were administered based on the investigator's judgment and the prescribing information. For subjects who entered the studies after starting the first dose of long-acting injectable aripiprazole in the hospital, if the initial injection was not 400 mg, the second injection should have been 400 mg, and thereafter, the monthly dose could be decreased to 300 mg, based on clinical judgment of the investigator.

For subjects who were psychiatrically stabilized and discharged prior to the completion of the required 14-day course of oral antipsychotic medication, a pre-discharge assignment was given to a CSW/SC. The CSW/SC maintained regular contact with the subject until the first outpatient visit in Phase B (Week 2), when oral aripiprazole was discontinued. Regular contact was defined as no less than weekly, but could have been more frequent depending on the clinical judgment of the CSW/SC and outpatient treatment team. Following the Week 2 Visit, subjects were to have contact with their assigned CSW/SC based on routine clinical care. Contact with the CSW/SC could be in person or by telephone, as clinically appropriate.

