## 9.1.4.3 Early Termination

All subjects who completed or withdrew from the study received a telephone call for safety follow-up at 30 ( $\pm$  5) days after the last study visit unless they withdrew their consent for participation in the study. This telephone contact was made to assess if there were any AEs experienced since the last visit. In addition, the subject was asked about any new medications or changes in existing medications and the information was documented in the source documentation. The study site registered the contact in the interactive voice response system or interactive web response system.

The end of the study was the date of the last study visit for the last subject.

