#### 9.5.1.5 Adverse Events and Other Events of Interest

An AE is any untoward medical occurrence in a subject or clinical investigation subject administered a drug under study. An AE does not necessarily have a causal relationship with the study drug. For this study, the study drug was aripiprazole once monthly and oral aripiprazole.

The criteria for identifying AEs were:

- Any unfavorable and unintended sign (including an abnormal laboratory finding), symptom, or disease temporally associated with the use of a drug under study, whether or not considered related to the drug under study
- Any new disease or exacerbation of an existing disease

Final; 26 Feb 2018 Page 40 of 80

LDL = low-density lipoprotein

a: Triglycerides were measured at screening only, to rule out exclusionary values

b: Serum β-hCG was performed if the subject or investigator suspected that the subject may be pregnant

- Any deterioration in nonprotocol-required measurements of a laboratory value or other clinical test (e.g., ECG or x-ray) that results in symptoms, a change in treatment, or discontinuation of study drug
- Recurrence of an intermittent medical condition (e.g., headache) not present pretreatment (i.e., baseline)
- An abnormal laboratory test result was considered an AE if the identified laboratory abnormality led to any type of intervention, whether prescribed in the protocol or not.

A laboratory result was to be considered by the investigator to be an AE if it:

- Resulted in the withdrawal of study drug
- Resulted in withholding of study drug pending some investigational outcome
- Resulted in an intervention, based on medical evaluation (e.g., potassium supplement for hypokalemia)
- Resulted in any out of range laboratory value that in the investigator's judgment fulfills the definitions of an AE with regard to the subject's medical profile

All AEs observed during the study were reported on the CRF. All AEs, regardless of relationship to study drug or procedure, were collected beginning from the time the subject signed the study ICF through the last visit. Serious AEs were collected for 30 days after the last dose or at the Follow-up Visit, whichever came later.

Abnormal laboratory values were not listed as separate AEs if they were considered to be part of the clinical syndrome that is being reported as an AE. Any laboratory abnormality considered to constitute an AE was reported as an AE on the CRF.

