#### 9.5.1.6 Serious Adverse Events and Other Events of Interest

An SAE was any untoward medical occurrence that at any dose:

- Resulted in death
- Was life-threatening (i.e., the subject was at immediate risk of death from the adverse event as it occurred; this did not include an event that, had it occurred in a more severe form or was allowed to continue, might have caused death)
- Required inpatient hospitalization or prolongation of existing hospitalization
- Resulted in persistent or significant disability or incapacity
- Was a congenital anomaly or birth defect in the child of a subject who was exposed to the study drug

Other important medical events that may not have been immediately life-threatening or resulted in death or hospitalization but, when based on appropriate medical judgment, may have jeopardized the subject or may have required intervention to prevent one of the outcomes in the definition of

Final; 26 Feb 2018 Page 42 of 80

SAE listed above should also have been considered SAEs. Medical and scientific judgment was to be exercised in deciding whether expedited reporting is appropriate in such situations.

In addition to the above, other events of interest included pregnancy or exposure to study drug through breastfeeding; AEs associated with study drug overdose, misuse, abuse, or medication error; and any treatment-emergent significant laboratory abnormality. These events of interest were to be captured using the SAE procedures but were to be considered SAEs only if they met one of the above criteria. All AEs associated with events of interest were to be reported on the CRF whether or not they met the criteria for SAEs.

The following hospitalizations were not considered to be SAEs because there is no "adverse event" (i.e., there is no untoward medical occurrence) associated with the hospitalization:

- Hospitalizations for respite care
- Planned hospitalizations required by the protocol
- Hospitalization planned before informed consent where the condition requiring the hospitalization had not changed post-study drug administration
- Hospitalization for administration of study drug or insertion of access for administration of study drug
- Hospitalization for routine maintenance of a device (e.g., battery replacement) that was in place before study entry

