## 9.5.1.7.4 Pregnancy Test

Women of childbearing potential and men who are sexually active must have used an effective method of birth control during the course of the study and for 30 days for a female subject and 90 days for a male subject after the last dose of SOC oral antipsychotics and 150 days for a female subject and 180 days for a male subject after the last dose of aripiprazole once monthly, in a manner such that risk of failure is minimized. Unless the subject and his or her partner(s) are sterile (i.e., women who have had an oophorectomy and/or hysterectomy or have been postmenopausal for at least 12 consecutive months; or men who have had orchiectomy) or remain abstinent, two of the following precautions must have been used: vasectomy, tubal ligation, vaginal diaphragm, intrauterine device, birth control pills, birth control injection, birth control implant, condom with spermicide, or sponge with spermicide. Any single method of birth control, including vasectomy and tubal ligation, could fail, leading to pregnancy.

Before enrolling women of child-bearing potential in this clinical study, investigators reviewed guidelines about study participation for women of childbearing potential. The topics generally included:

Final; 26 Feb 2018 Page 44 of 80

- General information
- Informed consent form
- Pregnancy prevention information
- Drug interactions with hormonal contraceptives
- Contraceptives in current use
- Guidelines for the follow-up of a reported pregnancy.

Prior to study enrollment, women of childbearing potential were advised of the importance of avoiding pregnancy during study participation and the potential risk factors for an unintentional pregnancy. The subject signed an ICF stating that the above-mentioned risk factors and the consequences were discussed with her.

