-  Safety clinical laboratory testing was conducted at screening, and as deemed clinically necessary thereafter. Standard clinical safety laboratory testing included: hematology (CBC with differential, and platelet count), chemistry (ALT, albumin, ALP, AST, total bilirubin, BUN, calcium, chloride, creatinine, glucose, potassium, serum prolactin, total protein, and sodium). Urinalysis was a dipstick with microscopic as clinically indicated.
- m: Exclusionary tests at screening were: platelets  $\leq 75,000 \text{ mm3}$ , Hgb  $\leq 9 \text{ g/dL}$ , fasting glucose > 126 mg/dL, HbA1c > 7.0%, absolute neutrophils  $\leq 1,000/\text{mm3}$ , ALT > 3x ULN, AST > 3x ULN, creatinine  $\geq 2 \text{ mg/dL}$ , diastolic blood pressure > 105 mm Hg, QTc > 475 msec on either the Bazett or Fridericia corrections on ECG, any other abnormal findings that would affect the safety of the subject or interpretation of the study results (Section 9.3.2).
- n: Lipid profile included: total cholesterol, HDL cholesterol, LDL cholesterol, and triglycerides.
- o: At screening the baseline C-SSRS was completed, at subsequent visits, the "since last visit" version was completed.
- P: All subjects received 14 days of oral aripiprazole beginning with the first dose of aripiprazole once monthly.
- q: All subjects who completed or withdrew from the study received a telephone call for safety follow-up at 30 (± 5) days after the last study visit unless they withdrew their consent for participation in the study to assess for any AEs experienced since the last visit (Section 9.1.4.3).
- r: Clinical laboratory testing only as needed for safety purposes, as determined by the Principal Investigator.

Final: 26 Feb 2018

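### For completers, the available text ends pregnancy and partner-pregnancy reporting about 30–35 days after the last depot injection, but requires contraception for 150 days (women) and 180 days (men).

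*Combined protocol and SAP*

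**What the plan says.** **What must be captured.** Section 9.5.4 lists exposure of an embryo or fetus as safety information. It covers maternal exposure and also "transmission of a medicinal product via semen following paternal exposure". Section 9.5.1.6 names pregnancy as an event of interest and adds: "These events of interest were to be captured using the SAE procedures".

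**How long it is captured.**
- Section 9.5.4: "Collection of safety information was completed from the first administration of the study drug until 28 days after discontinuation, unless otherwise specified in the protocol". That section also says that where two timeframes conflict, the longer one governs.
- Section 9.5.1.5: "Serious AEs were collected for 30 days after the last dose or at the Follow-up Visit, whichever came later".
- Table 3, footnote q: subjects who complete or withdraw, unless they withdraw consent, "received a telephone call for safety follow-up at 30 (± 5) days after the last study visit". Section 9.1.4.3 gives the purpose: "This telephone contact was made to assess if there were any AEs experienced since the last visit". It adds medication changes. Pregnancy is not mentioned.

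**How long precaution is required.** Section 9.5.1.7.4 requires contraception for "150 days for a female subject and 180 days for a male subject after the last dose of aripiprazole once monthly". For standard-of-care oral antipsychotics it asks for only 30 and 90 days.

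**When the last injection falls.** In Section 9.1.4.2, injections after baseline are due every 28 (-2, +5) "days at Weeks 4, 8, 12, 16, 20, and 24, totaling seven injections". Table 3 places Week 24 at Visit 8, Day 180, which is its last column.

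**Pregnancy tests.** Table 3 marks urine tests at screening and Visit 8. Its footnote e instead names screening, Visit 10 and a follow-up visit, with a serum test whenever pregnancy is suspected.

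**The concern.** The plan itself treats the depot as needing a long precaution after dosing: five months for women and six for men, far more than for oral drugs. It also says that exposure in pregnancy, including through the father, has to be captured. The collection rules, however, are ordinary SAE-type windows of about a month.

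A pregnancy or partner pregnancy conceived on, say, day 60 after a completer's last injection falls inside the contraception period. At that point no contact is scheduled and no collection rule in the available text still applies. It could go unreported. The stake is safety capture in the period after the last dose.

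**Working it through.** The plan states no figure of its own to reproduce. The check is date arithmetic on its rules, with day 0 as the last depot injection.

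**Inputs**

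| Input | Value | Source |
|---|---|---|
| General safety window | 28 days after discontinuation | 9.5.4 |
| SAE window, which also governs pregnancy | later of day 30 or follow-up contact | 9.5.1.5, 9.5.1.6 |
| Follow-up call | 30 ± 5 = 25 to 35 days after last visit | Table 3, footnote q |
| Completer's last injection | at the last visit, Week 24 | 9.1.4.2, Table 3 |
| Contraception after last injection | 150 days (women), 180 days (men) | 9.5.1.7.4 |

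**Step 1: end of collection for completers.** Last injection and last visit coincide, so the end is max(28, 30, 25 to 35) = day 30 to 35. The longer-timeframe rule is already applied here; 28 days is not the operative limit.

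**Step 2: period without a collection window** (contraception period minus end of collection)
- Women: 150 − 35 = 115 to 150 − 30 = 120 days.
- Men: 180 − 35 = 145 to 180 − 30 = 150 days.

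**Step 3: does the longer-timeframe rule import 150 or 180 days?** No. That rule reconciles collection periods. Section 9.5.1.7.4 places a duty on subjects and does not tell sites to collect or report anything for that long.

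**Step 4: does footnote e close the gap?** No. Table 3 ends at Visit 8, so there is no Visit 10, and the only follow-up described is a telephone call, at which no urine test can be done. Taken at face value, a test at follow-up would still fall at about day 25–35, at the start of the uncovered period, and would say nothing about partners of male subjects.

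**Step 5: is everything before day 30–35 captured?** Not necessarily. Collection depends on a pregnancy being known and mentioned. One conceived shortly before the call may not yet be recognised, and the call's stated content does not prompt for it.

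**Sensitivity (assumption).** Suppose the last injection fell on day 24 × 7 = 168 and the last visit on Day 180. The call would then come 12 + 25 = 37 to 12 + 35 = 47 days after the injection. The remainder is 150 − 47 = 103 to 150 − 37 = 113 days for women, and 180 − 47 = 133 to 180 − 37 = 143 days for men. The conclusion stands.

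**Withdrawn subjects.** If the last visit falls L days after the last injection, the call comes at L + 25 to L + 35, so collection can run later than for completers. L has no fixed limit, because Section 9.4.1 provides for gaps beyond five or six weeks. No single figure is given for this group.

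**The case against.** **The missing text may be exactly where a window would sit.** Section 9.5.4.1 refers SAE reporting to an agreement between investigator and sponsor, and its list of recipients is not in the copy available for review. Section 9.5.1.7.4 mentions guidelines on following up a reported pregnancy and a signed consent form, neither of which can be read here. This stands as a limit. A reader might infer that the trial had no longer pregnancy window anywhere; the documents do not support that. What can be said is that the readable rules state a window, and it is short. The absent part of 9.5.4.1 concerns SAE reporting, so a pregnancy window there is unlikely but possible.

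**No rule says reporting must match contraception.** True. The two periods have different purposes, and their difference is not a contradiction in the plan. Matching them is a design judgement. It rests on the plan's own decisions that this period needs precaution and that exposure in pregnancy is reportable.

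**Pregnancy is not ignored.** Also true. Section 9.3.3.3 withdraws a subject who becomes pregnant, such a pregnancy is reportable, and Section 9.5.4 accepts safety information from any source, so a pregnancy mentioned at the 30-day call would be recorded. The tempting reading that pregnancies are not captured at all is wrong; the gap lies after the call. Accepting any source widens where reports come from, not how long they are collected.

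**The size does not measure risk.** Agreed. The gap is a count of days. It gives no expected number of pregnancies, and expressing it as a percentage of the contraception period would suggest a precision about risk that the documents cannot supply.

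**The study is over.** The synopsis reports 9 subjects recruited and early termination. Nothing in the available text shows that a pregnancy was missed. The point concerns the plan's design.

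**Conclusion.** The concern holds for completers on the available text: a stated collection rule is too short for the risk period that the plan itself sets. The shortfall is about four months for women and five for men, preceded by a few weeks in which a new conception may go unrecognised.

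This rests on four readings: discontinuation in Section 9.5.4 means the last injection; pregnancy follows the SAE window because it follows the SAE procedures; the telephone call is the follow-up visit to which Section 9.5.1.5 refers; and no unread document sets a longer window. The last is the weakest, so confidence is moderate. The point is worth correcting but not critical: it affects only safety capture after the last dose, and no efficacy result changes.

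**What to change.** In Section 9.5.4, set a separate reporting window for pregnancy and partner pregnancy: 150 days after the last injection for women and 180 days for men.

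- Tell subjects to report a pregnancy until that date.
- Add a pregnancy and partner-pregnancy question to the existing 30-day call.
- Correct Table 3 footnote e so that its tests match visits that exist.
- A closing call at the end of the window is optional.
- Leave the SAE window unchanged.
- If the unread part of 9.5.4.1, the investigator–sponsor agreement or the consent form already sets such a window, cite it in 9.5.4 instead.

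The cost is protocol wording, one added question and, if chosen, one more call per treated subject. The downside is that site files stay open four to five months longer, for pregnancy reports only. With the study closed, this applies to any later protocol built on the same text.

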## 9.5.4.1 Reporting of Serious Adverse Events

All SAEs, regardless of their relationship to study treatment, were reported to the following according to the agreement between the investigator and the sponsor, [name], at Florida Atlantic University.

## 9.5.5 Completion/Discontinuation of Subjects

A subject could elect to discontinue the study at any time for any reason without prejudice. All subjects who discontinued the study were to complete the study's early discontinuation procedures indicated in the Schedule of Assessments (Table 3) whenever possible.

The investigator promptly explained to the subject involved that the study would be discontinued for that subject and provided appropriate medical treatment and other necessary measures for the subject. A subject who ceased to return for visits was followed up by mail, phone, or other means to gather information such as the reason for failure to return, the status of treatment compliance, the presence or absence of AEs, and clinical courses of signs and symptoms. This information was recorded in the CRF.

Subjects who discontinued early from the study were discontinued for one of these primary reasons: AE(s), lost to follow-up, subject choice, inadequate therapeutic effect, withdrawal of consent, pregnancy, study termination, or other (to be specified). In addition to the primary reason, the subject could indicate one or more secondary reasons for discontinuation.

A subject removed from the study for any reason could not be replaced.

## 9.5.6 Confirmation of Medical Care by Another Physician

The investigator instructed subjects to inform site personnel when they were planning to receive medical care by another physician. At each visit, the investigator asked the subject whether he or she had received medical care by another physician since the last visit or was planning to do so in the future. When the subject was going to receive medical care by another physician, the investigator, with the consent of the subject, informed the other physician that the subject was participating in the clinical study.

Final; 26 Feb 2018 Page 51 of 80

